4.2.4. Adjustments for Covariates

No formal statistical analysis that adjusts for possible covariate effects is planned.

Sponsor:	AxeroVision, Inc.		
Protocol:	AXR201901		
Document Version No.:	1.1	Document Date:	26-OCT-2020

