9.7. LEVEL OF SIGNIFICANCE

P-values will be descriptive in nature.

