4.2. General Statistical Methods and Data Handling

4.2.1. General Methods

All output will be incorporated into Microsoft Excel or Word files, sorted and labeled according to the International Conference on Harmonisation (ICH) recommendations, and formatted to the appropriate page size(s).

Tabulations will be produced for appropriate demographic, baseline, efficacy, and safety parameters. Baseline is considered to be the last assessment prior to first dose. For categorical variables, summary tabulations of the number and percentage within each category (with a category for missing data) of the parameter will be presented. For continuous variables, the mean, median, standard deviation, minimum and maximum values will be presented.

Formal statistical hypothesis testing will be performed on the VAS scores, Total MGD score, eyelid margin vascularity, LGS grade, conjunctival hyperemia, Schirmer score, TBUT, FCS, and OSDI with all tests conducted at the 2-sided, 0.05 level of significance. Summary statistics will be presented, as well as confidence intervals on selected parameters, as described in the sections below.

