 - Total MGD Score: the sum of secretion in 5 central glands on each individual eyelid will be evaluated, each will be scored from 0-3; 0 = clear/slightly yellow, 1 = opaque/yellow, whitish, particulate, 2 = paste, 3 = none/occluded; total score will range from 0-15
 - Vascularity of eyelid margin (Grade 0-4)
3. Change from baseline in average TBUT in AXR-270 Cream arms compared to Vehicle at Day 22. (TBUT is the number of seconds that elapse between the last blink and the appearance of the first dry spot in the tear film)

Sponsor:	AxeroVision, Inc.		
Protocol:	AXR201901		
Document Version No.:	1.1	Document Date:	26-OCT-2020

4. Change from baseline in upper lid horizontal length staining, longest sagittal width of staining, and LGS score of the eyelid margin in AXR-270 Cream arms compared to Vehicle at Day 22
5. Change from baseline in tFCS score (NEI/Industry Workshop; 0-15 scale) in the AXR-270 Cream arms compared to Vehicle at Day 22
6. Change from baseline in FCS (0-3 scale) by individual region (5 zones) in AXR-270 Cream arms compared to Vehicle at Day 22
7. Change from baseline in bulbar conjunctival hyperemia (0-4 scale) in AXR-270 Cream arms compared to Vehicle at Day 22
8. Change from baseline in OSDI score (0-100) in AXR-270 Cream arms compared to Vehicle at Day 22
9. Change from baseline in the modified BLISS score in AXR-270 Cream arms compared to Vehicle at Day 22
10. Change from baseline in the Schirmer score in AXR-270 Cream arm compared to Vehicle at Day 22

VAS scores, Total MGD score, eyelid margin vascularity, LGS grade, conjunctival hyperemia, Schirmer score, TBUT, FCS, and OSDI of the study eye/eyelid will be analyzed as continuous data. Analysis will be performed at each timepoint for the value at that timepoint and change from baseline using summary statistics. Change from baseline will also be analyzed with a longitudinal model with terms for baseline value and treatment.

The study eye/eyelid is the eye with the eligible eyelid having the worst (higher) score defined as the sum of the following two severity scores for the clinical signs of MGD at baseline:

1. Vascularity of eyelid margin
2. Total MGD Score

If both eyes, and eyelids, are eligible and have the same score, then select the right eye and upper eyelid. The non-study eyelid will only be the other eyelid(s) that meet all the eligibility rules that the study eyelid met as defined below.

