A study eye/eyelid is eligible if Inclusion Criteria #3, Inclusion Criteria #5, and Exclusion Criteria #3 are met for the same eyelid at Visit 1 and Visit 2.

Inclusion Criteria #3: Have a clinical diagnosis of moderate to severe MGD and who meet both of the following criteria, in at least one qualifying eyelid (upper and lower eyelid for each eye will be evaluated independently), at both Visit 1 (Screening) and again in the same eye/eyelid at Visit 2 (Randomization) examinations:

Sponsor:	AxeroVision, Inc.		
Protocol:	AXR201901		
Document Version No.:	1.1	Document Date:	26-OCT-2020

- a) Total MGD Score ≥ 5 and ≤ 14 (the sum of the individual score of 5 central glands on the upper and lower eyelids will be evaluated, each will be scored from 0-3: 0 = clear/slightly yellow, 1 = opaque/yellow, whitish, particulate, 2 = paste, 3 = none/occluded; total score will range from 0-15).
- b) Clinical sign severity score of at least 2 (moderate) on vascularity of the eyelid margin

Inclusion Criteria #5: Meet the following criteria, in both or the same qualifying eye as in Inclusion #3, at both Visit 1 (Screening) and Visit 2 (Randomization) examinations:

- a) tFCS score ≥ 3 and ≤ 14 in the NEI/Industry Workshop scale (0-15)
- b) Schirmer score of >7 mm without topical anesthesia

Exclusion Criteria #3: In the study eyelid, have greater than 4 glands that are not expressible from the 5 upper and/or 5 lower eyelid meibomian glands at both Visit 1 and Visit 2.

Least squares means for each treatment group and for the differences between 0.2% AXR-270 Cream and Vehicle, 2.0% AXR-270 Cream and Vehicle, and 0.2% AXR-270 Cream and 2.0% AXR-270 Cream will be presented from each model together with two-sided p-values and 95% confidence intervals at each post-baseline visit. The differences between Day 8 and baseline, Day 15 and baseline, and Day 22 and baseline for each treatment individually will also be presented from the model with two-sided p-values and 95% confidence intervals at each post-baseline visit.

Sample SAS longitudinal model code:

```

PROC MIXED DATA=INDATA;
  BY <EYE> <PARAMETER>; ** include <EYE> as applicable;
  CLASS <TREATMENT> <SUBJECT> <VISIT>;
  MODEL <ENDPOINT>=<TREATMENT> <VISIT> <TREATMENT>*<VISIT> <BASELINE>;
  REPEATED <VISIT> / SUBJECT=<SUBJECT> TYPE=UN;
  RANDOM Intercept;
  LSMEANS <TREATMENT>*<VISIT> / CL ALPHA=0.05;
  ESTIMATE '2.0 - Vehicle @ Day 8' <TREATMENT> -1 0 1
           <TREATMENT>*<VISIT> -1 0 0 0 0 0 1 0 0 /

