- Study Eye FCS Superior Zone (2 responder levels)
 - 0 Score
 - 1+ step improvement
- Study Eye FCS Temporal Zone (2 responder levels)
 - 0 Score
 - 1+ step improvement
- Study Eye Bulbar Conjunctival Hyperemia (2 responder levels)
 - 0 Score
 - 1+ step improvement
- OSDI (1 responder level)
 - <13 Score
- Study Eye Unanesthetized Schirmer Test (1 responder level)
 - >14 mm

Improvement as mentioned above means reduction in score.

Time to resolution will be defined as the duration between the date that a subject’s study eye/eyelid or subject, as appropriate per the endpoint (see Section 2.5.1), reaches a predefined “resolution” value post-baseline and the date of the first dose of study drug, i.e., (date of response – date of first dose) + 1. Time to resolution will be summarized by treatment. The differences, 95% CIs, and p-values, assuming equal variance (pooled), from a two-sample t-test will be provided for 0.2% AXR-270 vs Vehicle, 2.0% AXR-270 vs Vehicle, and 2.0% AXR-270 vs 0.2% AXR-270.

Counts and percentages of subjects/eyes that respond will be presented by treatment. P-values from a chi-squared test will be provided for 0.2% AXR-270 vs Vehicle, 2.0% AXR-270 vs Vehicle, and 2.0% AXR-270 vs 0.2% AXR-270.

By subject listings will be provided for each of the efficacy variables.

Change from baseline figures will be presented for the following:

- Eye discomfort VAS
- Eye dryness VAS
- Total MGD Score
- Vascularity of the eyelid margin
- Upper lid LGS
- tFCS
- Bulbar conjunctiva Hyperemia
- OSDI
- Modified BLISS
- Unanesthetized Schirmer Test

Sponsor:	AxeroVision, Inc.		
Protocol:	AXR201901		
Document Version No.:	1.1	Document Date:	26-OCT-2020

- IOP

The mean change from baseline by treatment will be plotted along the y-axis and visit along the x-axis. Standard deviation bars will be presented along with an asterisk (*) above or below the bars to indicate whether there is significance at an $\alpha=0.05$ level for the treatment compared to vehicle.

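### SAP 4.2.4 disclaims covariate adjustment although the longitudinal model adjusts for baseline, and the responder comparisons have unadjusted p-values with no between-arm difference or interval

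*SAP*

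**What the plan says.** **Covariates.** SAP 4.2.4 reads: "No formal statistical analysis that adjusts for possible covariate effects is planned". SAP 4.6 reads: "Change from baseline will also be analyzed with a longitudinal model with terms for baseline value and treatment". The sample code there has the model statement "MODEL <ENDPOINT>=<TREATMENT> <VISIT> <TREATMENT>*<VISIT> <BASELINE>". Least squares means, treatment differences, p-values and 95% confidence intervals at each post-baseline visit all come from this model.

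**Responders.** SAP 4.6 says: "Counts and percentages of subjects/eyes that respond will be presented by treatment". It continues: "P-values from a chi-squared test will be provided for 0.2% AXR-270 vs Vehicle", and likewise for the other two pairs of arms. It names no risk difference, ratio, interval or adjusted model, and no visit.

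**Time to resolution.** For this analysis, in the paragraph just before, the plan is fuller: "The differences, 95% CIs, and p-values, assuming equal variance (pooled), from a two-sample t-test will be provided".

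**Status of the tests.** SAP 4.2.1 has "all tests conducted at the 2-sided, 0.05 level of significance" for a list of continuous variables. Protocol 9.7 says: "P-values will be descriptive in nature". Both documents call all efficacy endpoints exploratory.

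**The concern.** There are two linked problems.

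First, 4.2.4 and 4.6 cannot both be right as written. SAP section 5, on changes to planned analyses, does not reconcile them.

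Second, where p-values are descriptive, the estimate and its interval carry the information, and for responders the plan supplies neither. It also leaves the collected baseline score out of the comparison. That matters most where response depends on where a subject starts:

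- **Already met at baseline.** Schirmer response is above 14 mm, while entry requires only more than 7 mm with no upper limit. TBUT response is at least 7 or 10 seconds, with no TBUT entry criterion. The five FCS zones, LGS and hyperemia have no entry minimum, so their score-0 level can hold before dosing. That makes 1 + 2 + 5 + 1 + 1 = 10 levels.
- **Out of reach from baseline.** A zone or hyperemia grade of 0 cannot improve by one step, and a low LGS score cannot improve by three. That makes 5 + 1 + 1 = 7 levels.

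For these 17 levels a chance baseline difference between arms of about 42 passes straight into the responder percentages.

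**Working it through.** **1. Arm sizes (SAP 2.1, 4.2.3).** 63 × 2/3 = 42 active and 63 × 1/3 = 21 vehicle per cohort. Pooled vehicle is 21 + 21 = 42, so each comparison is about 42 versus 42. LGS is done only at a subset of sites, so its arms are smaller. The plan gives no power, effect size, SD or response rate, so there is no stated figure to reproduce.

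**2. Number of levels (SAP 4.6).** In the order listed, from Eye Discomfort VAS to Schirmer: 6 + 6 + 2 + 2 + 2 + 2 + 2 + (5 × 2) + 2 + 1 + 1 = 36. Vascularity is labelled as one level but lists two. 36 × 3 comparisons = 108 p-values at any one timepoint. Fifteen levels are absolute thresholds (score 0, the two 100% VAS levels, TBUT, OSDI, Schirmer). Twenty-one are improvements from baseline, 10 of them on VAS.

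**3. What the missing interval would show.** The response rates here are assumed. Half-width = 1.96 × √[(p₁(1−p₁) + p₂(1−p₂))/42]. For 20% versus 40%: 1.96 × √[(0.16 + 0.24)/42] = 0.191. The range is 0.166 (10% versus 30%) to 0.210 (40% versus 60%), or about 17 to 21 points. Chi-squared power, with p̄ the mean of the two rates, is Φ{[|p₂−p₁| − 1.96√(2p̄(1−p̄)/42)] / √[(p₁(1−p₁)+p₂(1−p₂))/42]}. For 20% versus 40% this is Φ[(0.200 − 0.196)/0.0976] = 0.52. It is 0.46 for 30% versus 50%, and 0.80 for 30% versus 60%.

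**4. Power with and without baseline.** Simulation at 42 versus 42, two-sided 0.05 (assumed, because SAP 4.2.1 does not name the responder tests), 2000 to 2500 runs per setting, Monte Carlo error about 1 point. Uncorrected chi-squared is compared with the likelihood-ratio test for treatment in logit P(response) = β₀ + β₁·treatment + β₂·baseline. Assumed inputs: continuous baseline with mean 65, SD 15 or 20, limited to 35–100; outcome SD 15 or 20; shift 0.55 SD or 10 points; ordinal outcome on a 0–3 scale with a 0.55 SD latent shift. The continuous rows use baseline SD 15 and outcome SD 20. The last column covers all settings run.

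| Responder type | Correlation 0.3 | 0.5 | 0.7 | Change, points |
|---|---|---|---|---|
| Absolute threshold, continuous | 49.4 → 51.4% | 49.1 → 55.5% | 48.5 → 64.8% | +1 to +16 |
| Score 0, ordinal | 47.8 → 50.4% | 48.8 → 55.8% | 47.0 → 60.5% | +3 to +14 |
| 1+ step, ordinal | 34.4 → 44.4% | 44.5 → 51.7% | 61.8 → 67.0% | +5 to +10 |
| VAS 15+ points | 52.0 → 53.7% | 64.7 → 64.8% | 82.5 → 80.6% | -2 to +7 |
| VAS 30% | 57.4 → 56.2% | 66.0 → 64.3% | 76.6 → 76.6% | -2 to +4 |

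The VAS improvement levels gain little because baseline is already part of their definition. Type I error was 0.04 to 0.07 for both tests in the continuous-score settings where it was checked. The 2+ and 3+ step levels were not simulated separately.

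**5. Rare levels.** With 5% response in both arms and an assumed correlation of 0.6, the likelihood-ratio logistic test rejected a true null in 8.8% of runs, against 4.6% for chi-squared. Five percent of 84 subjects is about four responders.

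**The case against.** The case on the other side has real force:

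- **The contradiction may be wording only.** Text and code in 4.6 agree on the baseline term, so the model is unlikely to be programmed without it. That stands. One sentence cures it, and the plan as a whole does not waste the baseline score.
- **A reader might infer that no effect sizes are reported.** The documents do not support this. Every variable with a responder level is also in the longitudinal model, which gives baseline-adjusted differences with 95% CIs, and crude responder differences can be read off the per-arm percentages. What is missing is the responder difference as a planned estimate, with its interval.
- **A reader might infer that every responder comparison loses power.** The table shows otherwise for VAS percent improvement, and little for VAS points.
- **Adjusted logistic regression has its own risk.** That stands for rare levels. Total MGD Score 0 (entry score at least 5) or 100% VAS improvement could be that rare.
- **Upper or lower lid might seem a natural further covariate**, since protocol Appendix 3 describes different expression methods. That difference concerns gland expression only, and no benefit has been computed, so it is not proposed.
- **Stakes are low.** There is no power target. The responder analysis is an SAP addition (SAP section 5), and its table is not marked topline. This bears on priority, not on whether the point is right.

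**Conclusion.** The point holds in a limited form. That 4.2.4 and 4.6 conflict, and that the responder comparisons lack a between-arm difference and interval, follows from the text without assumptions. The loss from ignoring baseline is confined to absolute-threshold and ordinal-step levels. Its size, about 1 to 16 points of power, rests on assumed correlations of 0.3 to 0.7, assumed response rates, and the transfer of generic simulated scores to TBUT, OSDI and Schirmer. No stated figure in the plan is wrong. Priority is modest, because efficacy is exploratory and the p-values are descriptive.

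**What to change.** 1. **Reword SAP 4.2.4** to say that the baseline value of the endpoint is a covariate in the longitudinal model and in the responder models named in 4.6.
2. **Report the between-arm risk difference with 95% CI for every responder level.** For absolute-threshold and ordinal-step levels, fit a logistic model with treatment and baseline score. Predict each subject's response probability under each treatment, and average the difference. For VAS improvement levels an unadjusted difference with a score-type interval is enough. Keep chi-squared as supportive.
3. **Fix a sparse-cell trigger before unmasking**, as a minimum number of responders and of non-responders in the two arms compared, set clearly above the four or so responders at which the logistic test over-rejected. Below it, use the unadjusted difference with a score-type interval, or a penalised fit whose interval method is named.

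The cost is SAP wording, modest programming and the sparse-cell rule. No analysis planned in the protocol is displaced.

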4.2.5. Multiple Comparisons/Multiplicity

Multiplicity is not of concern for this study.

4.2.6. Subpopulations

No analyses of subgroups of subjects are planned.

4.2.7. Withdrawals, Dropouts, Loss to Follow-up

Subjects who withdraw from the study will not be replaced.

4.2.8. Missing, Unused, and Spurious Data

Any missing, unused, or spurious data will be noted in the final CSR. The data will be analyzed as recorded on the CRF. The last observation carried forward (LOCF) approach will be used to analyze incomplete datasets.

All data recorded on the CRF will be included in data listings that will accompany the clinical study report.

4.2.9. Visit Windows

Table 2 Evaluation Intervals for Efficacy Analysis

Evaluation	Protocol-Specified Interval	Interval for Analysis
Visit 1 (Day minus 14)	Day -16 to Day -12	Day -16 to Day -12
Visit 2 (Day 1)	Day 1	Day 1
Visit 3 (Day 8)	Day 6 to Day 10	Day 5 to Day 11
Visit 4 (Day 15)	Day 12 to Day 18	Day 12 to Day 18
Visit 5 (Day 22)	Day 19 to Day 25	Day 19 to Day 28

4.3. Interim Analyses

An interim analysis is not planned for this study.

4.4. Subject Disposition

Subject disposition will be tabulated by treatment group, including the number screened overall, the number and percent randomized, the number and percent dosed with 0.2% AXR-270 Cream, the number and percent dosed with 2.0% AXR-270 Cream, the number and percent dosed with Vehicle, the

Sponsor:	AxeroVision, Inc.		
Protocol:	AXR201901		
Document Version No.:	1.1	Document Date:	26-OCT-2020

number and percent that completed the treatment, the number and percent that discontinued treatment and the reasons for discontinuation, the number and percent that completed the study, the number and percent that discontinued prior to completing the study and the reasons for discontinuation, and the number in each subject population for analysis.

A summary will be provided for investigator enrollment by country, study center, and investigator name(s) by treatment dose and overall.

A by-subject listing of study completion information, including the reason for premature treatment and/or study discontinuation, if applicable, will be presented.

4.5. **Demographic and Baseline Characteristics**

Baseline and demographic information will be summarized for the FAS, PPS, and SAF using descriptive statistics by treatment group. Medical history will be summarized for the FAS by treatment group, where medical history includes systemic surgical, ocular surgical, systemic non-surgical, and ocular non-surgical history summarized separately by treatment group. No formal statistical comparisons will be performed.

Baseline, demographic, and medical history data will be provided in data listings.

4.6. **Efficacy Evaluation**

Efficacy analysis will be conducted using the FAS and PPS as outlined below.

All efficacy endpoints are exploratory in nature. The following endpoints will be considered to assess the efficacy of AXR-270 Cream on the study eye/eyelid.

1. Change from baseline in the following individual subject-reported symptoms using VAS (0-100 point scale) in the AXR-270 Cream (0.2% or 2.0%) arms compared to Vehicle at Day 22:
 - Eye Discomfort
 - Eye Dryness
2. Change from baseline in Investigator-related signs of MGD using individual severity scores in AXR-270 Cream arms compared to Vehicle at Day 22:
 - Total MGD Score: the sum of secretion in 5 central glands on each individual eyelid will be evaluated, each will be scored from 0-3; 0 = clear/slightly yellow, 1 = opaque/yellow, whitish, particulate, 2 = paste, 3 = none/occluded; total score will range from 0-15
 - Vascularity of eyelid margin (Grade 0-4)
3. Change from baseline in average TBUT in AXR-270 Cream arms compared to Vehicle at Day 22. (TBUT is the number of seconds that elapse between the last blink and the appearance of the first dry spot in the tear film)

Sponsor:	AxeroVision, Inc.		
Protocol:	AXR201901		
Document Version No.:	1.1	Document Date:	26-OCT-2020

4. Change from baseline in upper lid horizontal length staining, longest sagittal width of staining, and LGS score of the eyelid margin in AXR-270 Cream arms compared to Vehicle at Day 22
5. Change from baseline in tFCS score (NEI/Industry Workshop; 0-15 scale) in the AXR-270 Cream arms compared to Vehicle at Day 22
6. Change from baseline in FCS (0-3 scale) by individual region (5 zones) in AXR-270 Cream arms compared to Vehicle at Day 22
7. Change from baseline in bulbar conjunctival hyperemia (0-4 scale) in AXR-270 Cream arms compared to Vehicle at Day 22
8. Change from baseline in OSDI score (0-100) in AXR-270 Cream arms compared to Vehicle at Day 22
9. Change from baseline in the modified BLISS score in AXR-270 Cream arms compared to Vehicle at Day 22
10. Change from baseline in the Schirmer score in AXR-270 Cream arm compared to Vehicle at Day 22

VAS scores, Total MGD score, eyelid margin vascularity, LGS grade, conjunctival hyperemia, Schirmer score, TBUT, FCS, and OSDI of the study eye/eyelid will be analyzed as continuous data. Analysis will be performed at each timepoint for the value at that timepoint and change from baseline using summary statistics. Change from baseline will also be analyzed with a longitudinal model with terms for baseline value and treatment.

The study eye/eyelid is the eye with the eligible eyelid having the worst (higher) score defined as the sum of the following two severity scores for the clinical signs of MGD at baseline:

1. Vascularity of eyelid margin
2. Total MGD Score

If both eyes, and eyelids, are eligible and have the same score, then select the right eye and upper eyelid. The non-study eyelid will only be the other eyelid(s) that meet all the eligibility rules that the study eyelid met as defined below.

A study eye/eyelid is eligible if Inclusion Criteria #3, Inclusion Criteria #5, and Exclusion Criteria #3 are met for the same eyelid at Visit 1 and Visit 2.

Inclusion Criteria #3: Have a clinical diagnosis of moderate to severe MGD and who meet both of the following criteria, in at least one qualifying eyelid (upper and lower eyelid for each eye will be evaluated independently), at both Visit 1 (Screening) and again in the same eye/eyelid at Visit 2 (Randomization) examinations:

Sponsor:	AxeroVision, Inc.		
Protocol:	AXR201901		
Document Version No.:	1.1	Document Date:	26-OCT-2020

- a) Total MGD Score ≥ 5 and ≤ 14 (the sum of the individual score of 5 central glands on the upper and lower eyelids will be evaluated, each will be scored from 0-3: 0 = clear/slightly yellow, 1 = opaque/yellow, whitish, particulate, 2 = paste, 3 = none/occluded; total score will range from 0-15).
- b) Clinical sign severity score of at least 2 (moderate) on vascularity of the eyelid margin

Inclusion Criteria #5: Meet the following criteria, in both or the same qualifying eye as in Inclusion #3, at both Visit 1 (Screening) and Visit 2 (Randomization) examinations:

- a) tFCS score ≥ 3 and ≤ 14 in the NEI/Industry Workshop scale (0-15)
- b) Schirmer score of >7 mm without topical anesthesia

Exclusion Criteria #3: In the study eyelid, have greater than 4 glands that are not expressible from the 5 upper and/or 5 lower eyelid meibomian glands at both Visit 1 and Visit 2.

Least squares means for each treatment group and for the differences between 0.2% AXR-270 Cream and Vehicle, 2.0% AXR-270 Cream and Vehicle, and 0.2% AXR-270 Cream and 2.0% AXR-270 Cream will be presented from each model together with two-sided p-values and 95% confidence intervals at each post-baseline visit. The differences between Day 8 and baseline, Day 15 and baseline, and Day 22 and baseline for each treatment individually will also be presented from the model with two-sided p-values and 95% confidence intervals at each post-baseline visit.

Sample SAS longitudinal model code:

```

PROC MIXED DATA=INDATA;
  BY <EYE> <PARAMETER>; ** include <EYE> as applicable;
  CLASS <TREATMENT> <SUBJECT> <VISIT>;
  MODEL <ENDPOINT>=<TREATMENT> <VISIT> <TREATMENT>*<VISIT> <BASELINE>;
  REPEATED <VISIT> / SUBJECT=<SUBJECT> TYPE=UN;
  RANDOM Intercept;
  LSMEANS <TREATMENT>*<VISIT> / CL ALPHA=0.05;
  ESTIMATE '2.0 - Vehicle @ Day 8' <TREATMENT> -1 0 1
           <TREATMENT>*<VISIT> -1 0 0 0 0 0 1 0 0 /
           CL ALPHA=0.05;
  ESTIMATE '0.2 - Vehicle @ Day 8' <TREATMENT> -1 1 0
           <TREATMENT>*<VISIT> -1 0 0 1 0 0 0 0 0 /
           CL ALPHA=0.05;
  ESTIMATE '2.0 - 0.2 @ Day 8' <TREATMENT> 0 -1 1
           <TREATMENT>*<VISIT> 0 0 0 -1 0 0 1 0 0 / CL
           ALPHA=0.05;
  ESTIMATE 'Day 8 - Baseline for 2.0' <TIME> -1 0 1
           <TREATMENT>*<TIME> -1 0 1 0 0 0 0 0 0 /
           CL ALPHA=0.05;
RUN;

```

Sponsor:	AxeroVision, Inc.		
Protocol:	AXR201901		
Document Version No.:	1.1	Document Date:	26-OCT-2020

Where <TREATMENT> is sorted in ascending order of 0.2% AXR-270, 2.0% AXR-270, then Vehicle and <VISIT> is sorted in ascending order of Day 8, Day 15, and Day 22.

The variance-covariance structure (TYPE=) will be unstructured (UN). In the event that UN does not converge, then autoregressive (AR(1)) and compound symmetry (CS) will be used in that order until the model converges. A random subject intercept will also be included in the model (using Random INT statement in Proc mixed). An additional BY statement for eye will be added for endpoints that are evaluated by study/non-study eye.

Analysis of the non-study eye/eyelids will also be conducted on each of the above endpoints as supportive analysis.

If any values are missing for the study eye/eyelid, a sensitivity analysis will be conducted where missing values are imputed with the LOCF method.

In addition, time to resolution and responder analysis will be performed for the following efficacy variables:

- Eye Discomfort VAS (6 responder levels)
 - 20%, 30%, 50%, and 100% improvement
 - 10+ points and 15+ points improvement
- Eye Dryness VAS (6 responder levels)
 - 20%, 30%, 50%, and 100% improvement
 - 10+ points and 15+ points improvement
- Study Eyelid Total MGD (2 responder levels)
 - 0 Score
 - 3+ points improvement
- Study Eyelid Margin Vascularity (1 responder level)
 - 1+ step improvement
 - 2+ step improvement
- Study Eye TBUT (2 responder levels)
 - ≥7 seconds
 - ≥10 seconds
- Study Eye LGS Score (2 responder levels)
 - 0 Score
 - 3+ step improvement
- Study Eye tFCS (2 responder levels)
 - 0 Score
 - 3+ step improvement
- Study Eye FCS Central Zone (2 responder levels)
 - 0 Score
 - 1+ step improvement
- Study Eye FCS Inferior Zone (2 responder levels)
 - 0 Score

Sponsor:	AxeroVision, Inc.		
Protocol:	AXR201901		
Document Version No.:	1.1	Document Date:	26-OCT-2020

- 1+ step improvement
- Study Eye FCS Nasal Zone (2 responder levels)
 - 0 Score
 - 1+ step improvement
- Study Eye FCS Superior Zone (2 responder levels)
 - 0 Score
 - 1+ step improvement
- Study Eye FCS Temporal Zone (2 responder levels)
 - 0 Score
 - 1+ step improvement
- Study Eye Bulbar Conjunctival Hyperemia (2 responder levels)
 - 0 Score
 - 1+ step improvement
- OSDI (1 responder level)
 - <13 Score
- Study Eye Unanesthetized Schirmer Test (1 responder level)
 - >14 mm

Improvement as mentioned above means reduction in score.

Time to resolution will be defined as the duration between the date that a subject’s study eye/eyelid or subject, as appropriate per the endpoint (see Section 2.5.1), reaches a predefined “resolution” value post-baseline and the date of the first dose of study drug, i.e., (date of response – date of first dose) + 1. Time to resolution will be summarized by treatment. The differences, 95% CIs, and p-values, assuming equal variance (pooled), from a two-sample t-test will be provided for 0.2% AXR-270 vs Vehicle, 2.0% AXR-270 vs Vehicle, and 2.0% AXR-270 vs 0.2% AXR-270.

Counts and percentages of subjects/eyes that respond will be presented by treatment. P-values from a chi-squared test will be provided for 0.2% AXR-270 vs Vehicle, 2.0% AXR-270 vs Vehicle, and 2.0% AXR-270 vs 0.2% AXR-270.

By subject listings will be provided for each of the efficacy variables.

Change from baseline figures will be presented for the following:

- Eye discomfort VAS
- Eye dryness VAS
- Total MGD Score
- Vascularity of the eyelid margin
- Upper lid LGS
- tFCS
- Bulbar conjunctiva Hyperemia
- OSDI
- Modified BLISS
- Unanesthetized Schirmer Test

Sponsor:	AxeroVision, Inc.		
Protocol:	AXR201901		
Document Version No.:	1.1	Document Date:	26-OCT-2020

- IOP

The mean change from baseline by treatment will be plotted along the y-axis and visit along the x-axis. Standard deviation bars will be presented along with an asterisk (*) above or below the bars to indicate whether there is significance at an $\alpha=0.05$ level for the treatment compared to vehicle.

